In the case of treatment with a fixed dose, the patient is usually treated with a therapeutic dose of I-131 without performing a preliminary biodistribution study. However, in the case of treatment with the maximum safe dose of I-131 based on dosimetry, it is necessary to give an initial small dose of radioiodine, usually I-131, to measure the biodistribution of radioiodine and in turn to calculate the maximum dose that the patient can safely tolerate. The dilemma is that there is significant, but controversial, evidence that the initial small dose of I-131 may stun the thyroid metastases and decrease the uptake of the subsequent therapeutic dose of I-131, thus defeating the purpose of dosimetrically determining the maximum safe dose (4,10-20).

The radioisotope of iodine, I-123, is a pure gamma emitter and is thought to be less likely to cause stunning than I-131. However, there are some reports that even I-123 can cause stunning (21-24).

If it is demonstrated that I-123 does not cause significant stunning, a follow-up separately funded prospective study can be designed to determine whether a dosimetrically determined dose of I-131 is superior to a fixed dose. If an individually calculated maximum dose is determined to be superior, it would suggest that the dosimetric approach, which is currently used in only a

small minority of patients, should be offered to all patients. This would represent a major advance in the treatment of patients with metastatic differentiated thyroid cancer. Alternatively, if a dosimetrically determined dose of I-131 is not superior to a fixed dose, all patients can be treated with the simpler less costly fixed dose regimen.

III. Preliminary Studies/Progress Report: N/A

IV. Research Methods

A. Outcome Measure(s): Difference in uptake of I-123 in the thyroid remnant in the neck in the two imaging studies. Greater than a 20% decrease from the first to second study will indicate evidence of stunning.

B. Description of Population to be Enrolled:

Inclusion criteria:

1. Patient must be 21-years-old or greater.
2. Patient must be status post near total thyroidectomy for differentiated thyroid cancer without known distant metastases and who are planning to undergo routine remnant thyroid tissue ablation with I-131.
3. Patients must qualify for thyroid ablation with I-131.

Exclusion criteria:

1. Women who are pregnant or breastfeeding.
2. Prior bovine TSH use.
3. Known metastatic thyroid cancer.

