4. History of cardiovascular disease that may adversely affect patient participation at the discretion of the primary investigator.
5. Patients on hemodialysis.
6. Patients with acute serious illnesses at the discretion of the primary investigator.

C. Study Design and Research Methods: The proposed research will be the first study to perform test-retest studies in a group of patients to answer the long standing and fundamental question of whether diagnostic doses of I-123 cause stunning. Ten patients will be studied. If the patient elects to pursue participation in the study, the consent form will be explained to the patient

If the patient consents, the patient will undergo two I-123 whole body imaging studies prior to the I-131 thyroid remnant ablation.

Figure 1. General Scheme of Investigational Plan

The current standard of care is indicated in the solid black boxes and the additional research component is the dashed boxes.

[figure not shown]
[figure not shown]

Figure 2. Timing of standard of care and research interventions for the study population.

Patient Preparation

Participants will be placed on a low iodine diet for 1 week before the dosimetry study and continue on this diet until 24 hours after the therapeutic dose of ^{131}I .

Patient is prepared for the study by receiving an intramuscular injection of rhTSH (Thyrogen). The patients are prepared for receiving radioiodine by receiving an intramuscular injection of rhTSH (Thyrogen) on days 1, 2, 8, 9, 15 and 16 in order to raise the blood level of TSH and maximally stimulate the residual thyroid tissue to take up iodine (25-27). The Thyrogen received on days 1, 2, 8 and 9 will be provided free of charge by Genzyme. The subject's vital signs will be monitored before and after each Thyrogen injection. The Thyrogen injection will be withheld if vital signs show significant alterations from the patient's baseline.

Female patients of reproductive age who have not undergone a hysterectomy will undergo serum pregnancy tests on days 3 and 17 prior to administration of radioiodine.

All patients will have blood samples taken on days 3, 10, and 17 in the morning, to document that rhTSH was given and that there was a rise in thyroglobulin level (TSH action on thyroid cells) prior to administration of radioiodine.

Diagnostic imaging with I-123

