On days 3 and 10 the patient is given 3 mCi of ^{123}I orally in the morning. The participant will be asked to fast at least 4 hours before and 1 hour after the I-123 oral dose to control for interference with I-123 uptake.

Imaging with gamma camera from the top of the head to the thighs is performed on days 4 and 11.

In each of the I-123 whole body diagnostic imaging studies, one done for research purposes and the other as routine care, a region of interest will be placed over the I-123 uptake in the residual thyroid tissue and the number of counts will be recorded (28). Less than a 20% decrease in counts from the first to the second study will be considered no significant stunning (29). The Null hypothesis is that there will be less than a 20% decrease in I-123 in the thyroid remnant from the first to the second study.

In order to more accurately measure I-123 uptake in the residual thyroid tissue from the I-123 whole body diagnostic image, an I-123 standard will be placed in the field of imaging at the time of image acquisition. Use of I-123 standard is common practice for calibrating I-123 activity in the body. By using an I-123 standard, in addition to recording the number of counts in the residual thyroid tissue and comparing the count differences between the first and second study, percent uptake of I-123 in the residual thyroid tissue can be calculated for each study and compared. Less than a 20% decrease in percent uptake of I-123 in the residual thyroid tissue will be considered no significant stunning and provide additional supportive data to measuring counts in the residual thyroid tissue.

If thyroid cancer metastases are incidentally discovered in the patient with no known metastases, the patient will be removed from the study and referred back to Endocrinology.

Thyroid tissue ablation with I-131

On day 17, the patient is given a fixed therapeutic dose of ^{131}I determined by the endocrinologist and nuclear medicine physician (range 30-100 mCi ^{131}I).

Post-treatment imaging evaluation

Approximately 7 to 10 days after therapeutic dose of radioiodine (day 23-26), patient returns for routine, standard of care post ^{131}I treatment imaging.

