F. Data Analysis Plan: The primary endpoint will be measurement of thyroid remnant activity at 24 hours. We predict there will be less than a 20% reduction in the amount of I-123 in the thyroid remnant when the results of the second administered dose of I-123 is compared to the results from the first dose of I-123. The data will be analyzed statistically by the t-test and by the sign test. While we plan to study only 10 participants, this should be a sufficient number to determine whether there is any evidence of stunning by the sign test and, if there is stunning, whether there is more than a 20% stunning effect by the t-test. This is a pilot study, but it is likely to give results that are sufficiently definitive that it will not need to be repeated with larger numbers of participants. In addition, this is an internally funded research project that is intended to generate preliminary data to be

used in a larger NIH grant proposal that will compare fixed versus dosimetrically determined I-131 doses for treatment of patients with differentiated thyroid cancer with distant metastases.

G. Monitoring and Oversight

The sponsor investigator will be responsible for monitoring the trial per the trial monitoring plan, in addition to overseeing the safety and efficacy of the trial including any specimens collected, executing the data and safety monitoring (DSM) plan, and complying with all reporting requirements to local and federal authorities. This oversight will be accomplished through additional oversight from the Data and Safety Monitoring Committee (DSMC) at the University of Colorado Cancer Center (CU Cancer Center). The DSMC is responsible for ensuring data quality and study participant safety for all clinical studies at the CU Cancer Center, which is the coordinating institution of this trial. A summary of the DSMC's activities is as follows:

- Conduct of internal audits
- Ongoing review of all serious adverse events (SAEs), unanticipated problems (UAPs) and reportable adverse events (AEs)
- Has the authority to close and/or suspend trials for safety or trial conduct issues
- May submit recommendations for corrective actions to the CU Cancer Center's Executive Committee

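### The 20% rule appears to lead with uncorrected I-123 counts, although the trial already obtains percent uptake calibrated to a standard, which is the better variable to test

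*Combined protocol and SAP*

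**What the plan says.** All references are to the combined protocol and SAP.

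- **IV.C, Diagnostic imaging with I-123, counts.** Counts are recorded over the remnant on each scan, and the rule is set on them: "Less than a 20% decrease in counts from the first to the second study will be considered no significant stunning". The null hypothesis follows at once. It speaks only of I-123 in the remnant and does not say how that is measured.
- **IV.C, next paragraph, percent uptake.** A standard is placed in the field of view: "In order to more accurately measure I-123 uptake in the residual thyroid tissue from the I-123 whole body diagnostic image". The section adds: "Use of I-123 standard is common practice for calibrating I-123 activity in the body". The same 20% threshold is applied to percent uptake, which is there to "provide additional supportive data to measuring counts in the residual thyroid tissue".
- **IV.A.** The outcome is "Difference in uptake of I-123 in the thyroid remnant in the neck in the two imaging studies". Counts are not mentioned.
- **IV.F.** "The primary endpoint will be measurement of thyroid remnant activity at 24 hours". Then: "The data will be analyzed statistically by the t-test and by the sign test". The sign test is to detect any stunning and the t-test to judge whether it exceeds 20%. Neither test is tied to counts or to percent uptake.

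**The concern.** A count over the remnant depends on more than the fraction of the dose held there. It also varies with the activity actually given, the physical decay between dose and scan, and the camera's sensitivity that day. A standard in the same image, combined with assayed activities, removes these. IV.C gives accuracy as the reason for the standard but then ranks the calibrated result below the raw one.

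What is at stake is precision. There are ten pairs, and IV.F expects results definitive enough not to need repeating. Avoidable noise in the tested variable lowers the chance of showing that any fall is smaller than 20%. IV.F also leaves the reader to infer the tested variable from IV.C.

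**Working it through.** The documents give ten patients and the 20% threshold, but no SD, significance level, sidedness or power. There is no figure to reproduce.

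**1. What the standard removes.** Write remnant counts as C = S × A × U × 2^(−t/T), where S is camera sensitivity, A administered activity, U the fraction of the dose in the remnant, t the dose-to-scan time and T the half-life. A standard of activity A_s, referenced to the time of dosing, gives C_s = S × A_s × 2^(−t/T). Then (C / C_s) × (A_s / A) = U. Sensitivity and decay cancel, and assayed activities remove dose differences. Two things remain: biological uptake or washout if the two dose-to-scan intervals differ, and background counts.

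**2. Assumed inputs (none is in the documents).** Half-life 13.2 h; dose-to-scan time SD 1 h per scan; activity SD 5% per dose; residual error e of the percent-uptake ratio 5% (also 8%); biological test-retest SD b of the log ratio 15%, 20% or 30%; one-sided 5% t-test of the mean log ratio against ln 0.8, in the direction that shows a fall below 20%.

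**3. Extra noise in counts (SD of the log ratio).**
- Timing: (ln 2 / 13.2) × √2 × 1 = 0.0743.
- Activity: 0.05 × √2 = 0.0707.
- Combined: s = √(0.0743² + 0.0707²) = 0.1025.

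**4. Variance of counts relative to percent uptake, (b² + s²) / (b² + e²).**

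| b | e = 5% | e = 8% |
|---|---|---|
| 15% | 1.32 | 1.14 |
| 20% | 1.19 | 1.09 |
| 30% | 1.09 | 1.04 |

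Counts therefore need about 9-32% more pairs for equal precision, or 4-14% more if the residual error is 8%.

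**5. Power at a true 10% fall, n = 10.** Noncentral t with 9 df, critical value 1.833, noncentrality (ln 0.9 − ln 0.8) / (SD / √10), numerator 0.1178, e = 5%.

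| b | SD counts | Power counts | SD percent uptake | Power percent uptake |
|---|---|---|---|---|
| 15% | 0.182 | 60% | 0.158 | 70% |
| 20% | 0.225 | 46% | 0.206 | 51% |
| 30% | 0.317 | 29% | 0.304 | 30% |

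At b = 15% and e = 8%, percent uptake has 65%.

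**6. Do the two measures reach different test results?** I simulated 200,000 trials per setting, with the biological part shared by both measures and e = 5%. The table gives the share of trials in which one measure shows a fall significantly below 20% and the other does not.

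| True fall | b = 15% | b = 20% | b = 30% |
|---|---|---|---|
| None | 2.6% | 7.5% | 11.5% |
| 10% | 22.6% | 18.4% | 11.0% |

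Opposite significant conclusions (one measure significantly below a 20% fall, the other significantly above) did not occur in any of these trials.

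**The case against.** The strongest reply is that IV.C already gives an order. Counts are recorded, the rule is set on counts, the null hypothesis follows, and only then is percent uptake added as support. A supportive measure does not normally overrule the lead one. IV.A and IV.F may simply use general words for what IV.C makes operational. Nominal activity, morning dosing, fasting and next-day imaging are the same on both occasions. Timing details may be in the figure captioned "Figure 2. Timing of standard of care and research interventions for the study population", which is not shown, and count handling may be in reference 28.

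Most of this stands, and it rules out three stronger readings.

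- **That the plan makes no choice between the measures, or contradicts itself.** The documents do not support this. Counts lead by the natural reading of IV.C, and what is missing is a sentence in IV.F tying the tests to a variable.
- **That counts are biased.** Nothing shows a consistent difference in dose or timing between day 4 and day 11. Random differences mainly add noise.
- **That the choice could reverse the conclusion.** Under the assumptions above, opposite significant findings essentially never occur. What can differ is whether a result reaches significance.

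The reply does not explain why the calibrated measure, introduced for accuracy, should only support the uncalibrated one.

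**Conclusion.** The point holds as a cheap improvement, not as an error that undermines the trial. By its natural reading the plan tests counts, for which the readable text states no dose or decay correction, and gives second place to a better calibrated measure that it already collects. IV.F does not name the tested variable.

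The benefit depends on how large biological test-retest variation is beside dose and timing error, and the documents give neither. It could be worth about ten percentage points of power at a true 10% fall if biological variation is near 15%, and almost nothing if it is near 30%. If dosing and timing are tightly controlled, or the standard is measured poorly, the gain shrinks further. The textual finding is firm; the sizes are illustrative only.

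**What to change.** In IV.A, IV.C and IV.F, name one primary variable for both tests: the day 11/day 4 ratio of percent uptake at 24 hours.

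- **Calculation.** Percent uptake = 100 × (net remnant counts / net standard counts in the same image) × (assayed standard activity / assayed administered activity, both referenced to the same time), with no further decay correction.
- **Consistency.** Use the same region-of-interest rule, background rule and standard position on both scans. Record assayed activities and the assay, dose and scan times, and keep the dose-to-scan interval the same on both occasions, because the standard does not correct for biological change.
- **Tests.** Apply the t-test to the log ratio against ln 0.8 and the sign test to whether the ratio is below 1. These match the purposes IV.F gives the two tests.
- **Counts.** Report them descriptively and state that they do not alter the conclusion. Counts corrected for assayed activity and decay would be an acceptable alternative if named in advance as the single variable.

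The cost is protocol wording, recording of activities and times, a little more calculation, and a small error from measuring the standard. The standard is already in the field of view, so patients undergo nothing new.

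### The plan treats a fall of less than 20% as the null hypothesis, so neither planned test can show the absence of significant stunning, and the claim that 10 participants suffice has no stated basis

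*Combined protocol and SAP*

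**What the plan says.** Section I says that I-123 has to be proven to cause little or no stunning before it can serve as the comparator for other radioiodine isotopes. Section IV.A takes a decrease greater than 20% between the two studies as evidence of stunning. Section IV.C (Diagnostic imaging with I-123) gives the complementary rule, "Less than a 20% decrease in counts from the first to the second study will be considered no significant stunning", and then the hypothesis: "The Null hypothesis is that there will be less than a 20% decrease in I-123 in the thyroid remnant".

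Section IV.F names two analyses, the t-test and the sign test. On sample size it says "this should be a sufficient number to determine whether there is any evidence of stunning by the sign test". The second question it assigns to the same 10 participants is worded as follows: "if there is stunning, whether there is more than a 20% stunning effect by the t-test". It calls the study a pilot but adds that "it is likely to give results that are sufficiently definitive that it will not need to be repeated with larger numbers of participants".

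The sample size itself appears in section IV.C as "Ten patients will be studied". No section states an alpha, sidedness, power, assumed effect, SD of the within-patient change, or confidence interval. Section III reads "Preliminary Studies/Progress Report: N/A". If metastases are found incidentally, "the patient will be removed from the study and referred back to Endocrinology"; no replacement rule is given.

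**The concern.** The result the investigators hope to report is the null hypothesis. A test of that null can produce evidence of a fall of more than 20%, but not evidence against one. With 10 patients, a non-significant result may mean no stunning or merely an imprecise estimate, and nothing in the plan separates the two. The follow-up trial described in sections II and H depends on demonstrating that I-123 causes no significant stunning.

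The sufficiency wording adds to this. A reader of the final report would take from section IV.F that 10 patients had been judged enough for a near-definitive answer, although none of the quantities needed for that judgement is given.

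**Working it through.** **Inputs from the documents.** n = 10 pairs (IV.C); threshold 20% (IV.A, IV.C); sign test and t-test (IV.F). The plan gives no calculation for n = 10, so there is no figure to reproduce.

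**Assumptions.** Alpha 5%; within-patient percent change normal with SD 10, 15, 20 or 30 points; no ties; all 10 pairs evaluable; the 20% threshold applied to the mean, as a t-test does.

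**Step 1: what each planned analysis can conclude.**
- Sign test: null of no tendency to fall. Rejection shows some fall. Non-rejection shows nothing about 20%.
- t-test against 20%: null of a fall below 20%. Rejection shows a fall of more than 20%. Non-rejection leaves the null standing without support.
- The IV.A/IV.C criterion applied to the observed mean: with a symmetric distribution and a true fall of exactly 20%, the observed mean is below 20% with probability 0.5, whatever the SD or sample size.

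None of the three requires a fall of 20% or more to be excluded. This step needs no SD.

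**Step 2: sign test with n = 10.** Under Binomial(10, 0.5), P(at least 8 decreases) = 56/1024 = 0.0547 (two-sided 0.109) and P(at least 9) = 11/1024 = 0.0107 (two-sided 0.0215). At 5%, one- or two-sided, at least 9 of 10 must decrease.

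Power = 10p⁹(1 − p) + p¹⁰, with p = Φ(mean fall/SD). For a true mean fall of 20%:

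| Assumed SD | p | Power |
|---|---|---|
| 10 | 0.977 | 98% |
| 15 | 0.909 | 77% |
| 20 | 0.841 | 51% |
| 30 | 0.748 | 24% |

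**Step 3: the 95% CI judged against 20%.** Half-width = t(0.975, 9) × SD/√10 = 2.262 × SD/3.162. Power comes from the noncentral t on 9 df with noncentrality (distance of the true fall from 20)/SD × √10. For example, at SD 20 and zero true change the noncentrality is 20/20 × 3.162 = 3.16 and the power is 80%.

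| Assumed SD | CI half-width | Excludes a 20% fall, true change 0 | Excludes a 20% fall, true fall 10% |
|---|---|---|---|
| 10 | 7.2 | >99% | 80% |
| 15 | 10.7 | 96% | 47% |
| 20 | 14.3 | 80% | 29% |
| 30 | 21.5 | 47% | 16% |

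At zero true change, 80% power holds up to an SD of 20.1 points. With 8 evaluable pairs the third column becomes >99%, 90%, 68% and 37%.

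**Step 4: what the CI rule costs.** At a true fall of exactly 20%, each tail is 2.5%, so 100 − 2 × 2.5 = 95% of trials are inconclusive. At zero true change the inconclusive share is 100% minus the third column of step 3. For a true 30% fall:

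| Assumed SD | Inconclusive, true change 0 | Inconclusive, true fall 30% | Declares >20%, one-sided 5% t-test, true fall 30% | Declares >20%, 95% CI rule, true fall 30% |
|---|---|---|---|---|
| 10 | about 0% | 20% | 90% | 80% |
| 15 | 4% | 53% | 62% | 47% |
| 20 | 20% | 71% | 43% | 29% |
| 30 | 53% | 84% | 25% | about 16% |

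**The case against.** The strongest reply is that this is a 10-patient pilot meant to generate preliminary data for a grant, and that the design controls variability through within-patient pairing, a low-iodine diet, fasting and an I-123 standard in the field of view. If these keep the SD small, 10 patients may be ample. That is right as far as it goes: step 3 shows that 10 pairs can exclude a 20% fall if the true change is near zero and the SD is about 20 points or less. It does not rescue the direction of the null, and the pilot label sits badly with the statement that the study will probably not need repeating.

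Two stronger readings are tempting and should not be made:

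- A reader might infer that the sign test is a formal gate for the t-test. The clause about stunning being present occurs in a sentence on what 10 participants can determine, while the analysis sentence itself names both tests without condition. Gating would also hardly matter: for a true 30% fall, t-test power without and with a gate is 43% and 43% at SD 20, and 25% and 24% at SD 30.
- A reader might infer that a non-significant sign test is the plan's rule for no stunning, and so count the shortfall in sign-test power as wrong conclusions. No section says this. The only stated criterion is the 20% threshold.

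A further objection is that the CI rule's 2.5% error at a true 20% fall is true by construction. It is; the case for the rule is that it answers the question posed in section I.

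**Conclusion.** The point holds, as a change the plan should make. The planned tests cannot establish what section I requires, because the hoped-for result is the null and no rule excludes a fall of 20% or more. That conclusion rests on the documents alone. Applied to the observed mean, the 20% criterion would pass a true 20% fall about half the time; this needs only symmetry.

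The sufficiency claim is unsupported rather than shown to be false. A reader might conclude that 10 patients are too few, but the documents give no SD from which to say so. Over assumed SDs of 10 to 30 points, sign-test power at a true 20% mean fall runs from 98% to 24%, and power to exclude a 20% fall at zero true change from over 99% to 47%. These figures depend on the assumed alpha, SDs and normality.

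**What to change.** 1. In section IV.C, reword the null as a mean fall of 20% or more.
2. In section IV.F, state alpha and sidedness.
3. Base the main conclusion on the paired mean percent change with its 95% CI. Conclude no significant stunning only if the CI excludes a fall of 20% or more; conclude a fall of more than 20% only if the whole CI lies beyond 20%; otherwise report the result as inconclusive.
4. Keep the sign test as supportive, and state that a non-significant result is not evidence of no stunning.
5. Replace the wording on a sufficient number and on not needing repetition with the SD range over which n = 10 can exclude a 20% fall: 80% power at zero true change up to an SD of about 20 points.

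This needs no extra patients, scans or measurements. It does change the hypothesis under test, so sections IV.C and IV.F must be amended together. The plan should also disclose the inconclusive rates and the loss of power to declare a true 30% fall shown in step 4, and that a t-based interval is more sensitive to skew than the sign test.

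### IV.F lets the sign test decide whether there is evidence of stunning, apparently against zero change, while IV.A and IV.C put that threshold at a 20% fall, and no section says which test settles the aim

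*Combined protocol and SAP*

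**What the plan says.** Three parts of section IV bear on this.

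- IV.A, Outcome Measure(s): "Greater than a 20% decrease from the first to second study will indicate evidence of stunning".
- IV.C, under diagnostic imaging: "Less than a 20% decrease in counts from the first to the second study will be considered no significant stunning". The same paragraph continues: "The Null hypothesis is that there will be less than a 20% decrease in I-123 in the thyroid remnant".
- IV.F, Data Analysis Plan, names a t-test and a sign test. Of the 10 participants it says "this should be a sufficient number to determine whether there is any evidence of stunning by the sign test". The sentence then gives the t-test a second question: "if there is stunning, whether there is more than a 20% stunning effect by the t-test".

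The plan states no null value for the sign test, no alpha or sidedness, no SD for the within-patient change, and no rule for combining the two tests.

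**The concern.** In IV.A, evidence of stunning already means a fall above 20%. In IV.F, the sign test establishes evidence of stunning first, and only then is it asked whether the effect exceeds 20%. The second question would be redundant under IV.A's definition, so IV.F must be using a lower threshold. A paired sign test by default asks whether falls and rises are equally likely, which is a null of zero change.

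Any true fall between 0% and 20% therefore satisfies IV.C's null but violates the sign test's null. A small, consistent fall could be reported as evidence of stunning under IV.F and as not meeting that description under IV.A. The specific aim is to determine whether I-123 causes stunning, and sections II and IV.H make a follow-up study depend on the answer, so the label given to that result matters.

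**Working it through.** **The plan's own figure.** The only figure is 10 participants, called sufficient. It comes with no alpha, power, SD or effect size, so it cannot be reproduced.

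**Inputs.** From the plan: n = 10 pairs and the 20% threshold. Assumed: no ties, normally distributed per-patient percentage falls, a 5% level, and an SD of 5 to 40 percentage points.

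**Step 1: sign test rejection rule (null of zero change).**
- P(9 or more falls of 10) = (10 + 1)/1024 = 0.0107 one-sided, 0.0215 two-sided.
- P(8 or more) = (45 + 10 + 1)/1024 = 0.0547 one-sided, 0.1094 two-sided.

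At 5% the rule is 9 or more falls, whether one- or two-sided.

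**Step 2: chance of a significant sign test.** With true mean fall d and standard deviation SD, each patient shows a fall with probability p = Φ(d/SD). The test rejects with probability 10p⁹(1 − p) + p¹⁰. For d = 10 and SD = 10: p = Φ(1) = 0.8413, giving 0.335 + 0.178 = 0.513.

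| True fall | SD 5 | SD 10 | SD 15 | SD 20 | SD 25 | SD 30 | SD 40 |
|---|---|---|---|---|---|---|---|
| 5% | 51% | 14% | 7% | 5% | 4% | 3% | 2% |
| 10% | 98% | 51% | 24% | 14% | 9% | 7% | 5% |
| 15% | 100% | 86% | 51% | 30% | 19% | 14% | 8% |

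Every row satisfies IV.C's null. The rate passes one half only when the true fall is about 0.99 SD or more.

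**Step 3: the t-test against 20%.** T = (mean fall − 20)/(s/√10), rejecting above 1.833 (one-sided 5%, 9 degrees of freedom). Rejection follows from the noncentral t with noncentrality (d − 20)/(SD/√10); for d = 25 and SD = 10 this is 5/3.162 = 1.581.

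| True fall | SD 10 | SD 15 | SD 20 | SD 25 |
|---|---|---|---|---|
| 15% | 0.1% | 0.4% | 0.9% | 1.3% |
| 20% | 5% | 5% | 5% | 5% |
| 25% | 42.7% | 25.2% | 18.1% | 14.5% |

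Over SD 5 to 40, rejection is at most 2.2% for true falls of 15% or less and about 4% at 19%. Requiring a significant sign test first can only lower these rates.

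**Step 4: how often the labels diverge.** By simulation at a true 15% fall, the sign test is significant and the observed mean fall is under 20% in 80%, 38%, 15% and 6% of trials at SD 10, 15, 20 and 25. This applies the 20% rule to the group mean; IV.C does not say whether its rule is for the mean or for each patient.

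**The case against.** The strongest reply is that IV.F is a coherent two-step plan: first whether there is any fall, then whether it exceeds 20%. The t-test in the same sentence handles the 20% question and, as step 3 shows, rarely makes a wrong claim of more than 20%. IV.C says no *significant* stunning, section I speaks of little or no stunning, and sections II and IV.H again use the word significant. These support a graded reading, in which some stunning below 20% is possible but not significant.

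Much of this stands. A reader might infer that the plan often produces false positives. The documents do not support that: the sign test's zero null is inferred, and rejecting it when uptake truly fell by 10% or 15% is a correct rejection of that null. The rates in step 2 become error rates only if the sign test is taken as the test of IV.C's null, which no section says. A reader might also infer a direct contradiction between IV.F and IV.C; the graded reading answers that.

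The reply does not remove the conflict with IV.A, which attaches evidence of stunning to a fall above 20% without the qualifier. Nor does it supply a rule for which test answers the aim. If the sign test was meant to be centred at 20%, IV.F would still have to say so.

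**Conclusion.** The point holds as a conflict of definition between IV.A and IV.F, with IV.C's null on IV.A's side, and as a missing decision rule. That part rests on the text and needs no assumption about the SD.

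Its size is conditional. If a significant sign test is reported as evidence of stunning, the label attaches to a true 10% fall in about 9% to 51% of trials and to a true 15% fall in about 19% to 86%, for SD 25 down to 10 points. For the 10% fall the rate is 98% at SD 5 and 5% at SD 40, so the plan does not support a general statement that small falls would often be called stunning. These figures assume normal percentage falls, 10 untied pairs, a 5% level and a zero null for the sign test. If the conclusion rests on the t-test, wrong claims of more than 20% stunning stay at or below about 5%.

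It should be corrected before analysis, because the trial's single aim turns on this label.

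**What to change.** Amend IV.F as follows.

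1. State the null value, alpha and sidedness of each test.
2. Name the one-sample t-test of the percentage fall against 20% as the test of IV.A's definition, and run it whatever the sign test shows.
3. Keep the sign test against zero, but report its result as any fall in uptake and not as evidence of stunning.
4. Report the mean percentage fall with its confidence interval, and state that a non-significant t-test is not proof of no stunning.

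The cost is wording only: no extra patients, scans or data. There are two downsides. A consistent fall under 20% would be reported only as a fall in uptake. The t-test also has little power just above the threshold: at a true 25% fall, which is stunning under IV.A, it rejects in 42.7%, 25.2%, 18.1% and 14.5% of trials at SD 10, 15, 20 and 25. Item 4 guards against misreading that. The 95% interval has half-width 2.262 × SD/√10, about 7 points at SD 10 and 18 points at SD 25, so the reader can see what the data leave open.

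Centring the sign test at 20% instead would also align the definitions, but at a true 30% fall its power is only 51% at SD 10 and 24% at SD 15, against 90% and 62% for the t-test. It could serve only as support.
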